This clinical trial aims to investigate the effectiveness of a Cognitive Behavioural Therapy (CBT) program delivered via a smartphone application (called *ClearlyMe*) for improving mental health outcomes in Australian adolescents (aged 12 to 17 years) with mild to moderate depressive symptoms.

This trial will examine the effectiveness of a new CBT smartphone application (*ClearlyMe*) for reducing depressive symptoms in adolescents when compared to guided use and an active-attention matched control condition.

The primary outcome is depressive symptoms, measured by a change in self-report symptoms between baseline and 6-weeks post-baseline (primary endpoint). Secondary mental health outcomes include improvements in anxiety symptoms, psychological distress and emotional wellbeing between baseline and 6-weeks post-baseline as measured by validated self-report scales. Follow-up outcomes will be evaluated at 4-months post-baseline (secondary endpoint) using the same self-report scales to determine whether effects are sustained in the mid-term and whether the interventions are associated with any delayed benefits or harms.

The primary research questions that this trial seeks to address are:

1. What is the effectiveness of *ClearlyMe* (both self-directed and guided use) for reducing depressive symptoms?

Secondary research questions include:

2. What is the effectiveness of *ClearlyMe* for reducing anxiety symptoms, psychological distress, rumination, and improving emotional wellbeing, quality of life, emotion regulation, and CBT skill acquisition?
3. Does guided support lead to greater engagement with and completion of the *ClearlyMe* app when compared to self-directed use?
4. Do factors such as gender, age, baseline mental health history or symptom severity, perceived need for care or openness to digital mental health, moderate the improvements in depressive symptoms found among users of *ClearlyMe*?
5. Do factors such as rumination, emotion regulation, CBT skill acquisition, digital therapeutic alliance and program engagement/completion mediate the improvements in depressive symptoms found among users of *ClearlyMe*?

Primary and Secondary Hypotheses:

This trial will determine whether the *ClearlyMe* smartphone application is effective for lowering depressive symptoms when compared to guided use and an active attention-matched control in symptomatic adolescents. It is hypothesised that:

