H1= Participants who receive *ClearlyMe* (both self-directed and guided use) will report greater reductions in depressive symptoms between baseline and primary endpoint as well as baseline and secondary endpoint when compared to participants in the control condition;

H2= Participants who receive *ClearlyMe* (both self-directed and guided use) will report greater improvements in secondary outcomes (anxiety, psychological distress, emotional wellbeing,

quality of life, rumination, emotion regulation and CBT skill acquisition) between baseline and primary endpoint as well as baseline and secondary endpoint when compared to participants in the control condition;

H3= Participants' engagement with and completion of *ClearlyMe* will be significantly higher among participants who receive guided support when compared to participants who receive self-directed use.

Other exploratory hypotheses:

H4= Improvements in depressive symptoms among users of *ClearlyMe* will be moderated by gender, age, history of mental health, symptom severity at baseline, greater perceived need for care and higher levels of openness to digital mental health.

H5= Improvements in depressive symptoms among users of *ClearlyMe* will be mediated by rumination, emotion regulation, CBT skill acquisition, digital therapeutic alliance, and rates of engagement/completion.

5. Background Information

Adolescence is a significant and sensitive stage of life, whereby individuals evolve physically, socially, and psychologically as they transition to adulthood (Dahl et al., 2018). Given the rapid changes in a young person's development, this period also presents important risks and opportunities for young people's mental well-being. For example, a young person's access to a supportive environment, ability to maintain healthy sleeping and exercise behaviours, learn and develop coping, problem solving, emotional and interpersonal skills can influence their mental health (WHO., 2020). Poor mental health can have detrimental consequences to a young person's quality of life and their ability to function socially and academically (McGorry et al., 2011; Patel et al., 2007). Recent research suggests the global prevalence of depressive and anxiety symptoms in children and adolescents during the COVID-19 pandemic has increased, with 1 in 4 experiencing elevated depressive symptoms and 1 in 5 experiencing elevated anxiety symptoms, highlighting the need for mental health care (Racine et al., 2021).

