This study will utilise a three-arm randomised controlled trial, conducted entirely online via the Black Dog Institute Research Engine. Data will be assessed at baseline, primary endpoint (6-weeks post-baseline) and secondary endpoint (4-months post-baseline). This methodology is appropriate to meet the research aims because RCTs are considered to provide the most reliable evidence on the effectiveness of interventions because the processes used during the conduct of this type of trial minimise the risk of confounding factors influencing the results. Because of this, the findings generated by RCTs are likely to be closer to the true effect than the findings generated by other research methods (Akobeng, 2005).

Randomisation will be carried out according to the International Council for Harmonisation (ICH) guidelines. Randomisation to one of the three trial arms will be conducted immediately after completion of the baseline assessment using a computerised randomisation procedure within the Black Dog Institute Research Engine. Stratified randomisation approach with a block size of 6 (1:1 ratio) will be used to ensure balance across the conditions in terms of age (12 to 14 years vs. 15 to 17 years), ~~gender (male vs. female)~~, and symptom severity (mild [as determined by a total score of 9 or less on the PHQ-A] vs moderate to moderately-severe [as determined by a total score of 10 or more on the PHQ-A]). Allocation will be fully automatic, with no interference from the research team.

Blinding – Participants: All study materials will refer to the interventions being examined as “smartphone activities and information for your mental health”. While participants will be aware of which smartphone activity they will be required to use (due to the PICF and instructions for use provided), they will not be directly informed of their condition allocation (i.e., intervention 1 vs. intervention 2 vs. control).

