An additional study assessment will occur at follow-up, with the secondary endpoint assessed at 4-months post-baseline. At secondary endpoint, participants will be invited to complete the primary endpoint assessment via an automated email/SMS invitation generated by the Black Dog Institute Research Engine. The outcome measures assessed at primary endpoint are outlined in Appendix D. The primary endpoint assessment is entirely self-report. It will take approximately 20 minutes to complete and can be completed on any Internet-enabled device. Participants will have 7 days to complete the primary endpoint assessment (from invitation date) and will receive two reminders to complete the assessment (sent day 3 and day 5). Upon completion of the secondary endpoint assessment, trial participation will cease. Participants will be thanked for their time and provided with additional information on mental health and help-seeking resources.

Young people will be reimbursed for the time taken to complete the study assessments. Participants will be reimbursed \$10AUD (electronic gift voucher) for completion of the baseline, post-test and follow-up assessments. The total possible reimbursement will be \$30AUD, which will be emailed and sent via SMS to participants within 14 days of their completion of the scheduled assessment. These amounts are aligned with the best-practice wage-payment model (Dickert & Grady 1999) such that participants are paid for time taken to participate in the study, using the current minimum wage of \$19.84p/hr. In addition, participants allocated to trial arm 2 (guided use of ClearlyMe) will be reimbursed an additional 25AUD (GiftPay Voucher sent by email and SMS) upon randomisation to this group to cover the cost sending and receiving SMSs. This amount was based on the estimated costs of approximately 12 SMS sent per week at \$0.30 per message. Because of this incentive, data integrity checks will be embedded into the online assessments to check for duplicate users at baseline (e.g., emails, and mobile number checks) and to ensure that standards of internet studies are met (Reips, 2002).

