9. Do factors such as gender, age, baseline mental health history or symptom severity, openness to digital mental health, digital therapeutic alliance, perceived need for care, moderate the improvements in depressive symptoms found among users of *ClearlyMe*?
10. Do factors such as CBT skill acquisition, emotion regulation, rumination, and program engagement/completion mediate the improvements in depressive symptoms found among users of *ClearlyMe*?

Data

All participants will complete self-report questionnaires, including:

- Demographics (baseline only)
- Depressive symptoms (Patient Health Questionnaire: Adolescent version; PHQ-A; baseline, primary, secondary endpoints)
- Anxiety symptoms (Generalised Anxiety Disorder-7; GAD-7; baseline, primary, secondary endpoints)
- Psychological distress (Distress Questionnaire-5; DQ-5; baseline, primary, secondary endpoints)
- Emotional wellbeing (The Short Warwick-Edinburgh Mental Well-being Scale; SWEMWBS; baseline, primary, secondary endpoints)
- Perceived need and help-seeking barriers (Perceived Need for Care Questionnaire; PNCQ; baseline, primary, secondary endpoints)
- CBT skill acquisition (Cognitive Behavioural Therapy Skills Questionnaire; CBTSQ; baseline, primary, secondary endpoints)
- Quality of life (The Child Health Utility 9D; CHU-9; baseline, primary endpoints)
- Emotion regulation (Emotion Regulation Questionnaire for Children and Adolescents; ERQ-CA; baseline, primary, secondary endpoints)
- Rumination (Ruminative Response Scale; RRS-short form; baseline, primary, secondary endpoints)
- Digital therapeutic alliance (Digital Working Alliance Inventory; D-WAI; primary endpoint)
- Digital program satisfaction (Digital program satisfaction; Satisfaction Questionnaire; primary endpoint)
- Digital program barriers (Digital program barrier; Barriers Questionnaire; primary endpoint)
- Recent mental health care (Mental Health Care Questionnaire; primary endpoint)

Intervention use will be measured automatically for each digital intervention. Participants use of the *ClearlyMe* app will be measured by collecting data collected including lessons completed, collections completed, features accessed, total time spent in app, content liked/disliked, content saved, and individual responses to lesson activities.

Participants use of the psychoeducational content will be measured through Google analytics tracking the number of times the URL within the SMS is clicked on.

Trial Management Group (TMG)

Overview

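### The protocol contradicts itself on whether quality of life (CHU-9) is measured at 4 months; under the Appendix I list, one component of H2 would have no data

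*Protocol*

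**What the plan says.** Section 4 states H2 for seven secondary outcomes: anxiety, psychological distress, emotional wellbeing, quality of life, rumination, emotion regulation and CBT skill acquisition. The time frame covers both follow-ups: "quality of life, rumination, emotion regulation and CBT skill acquisition) between baseline and primary endpoint as well as baseline and secondary endpoint". Section 7 defines these as "primary endpoint (6-weeks post-baseline) and secondary endpoint (4-months post-baseline".

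Three other places bear on what is collected at 4 months.

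- Section 4, objectives: "Follow-up outcomes will be evaluated at 4-months post-baseline (secondary endpoint) using the same self-report scales".
- Section 10, paragraph on the 4-month visit: "At secondary endpoint, participants will be invited to complete the primary endpoint assessment". For the measures it refers to Appendix D.
- Appendix I, Data: "Quality of life (The Child Health Utility 9D; CHU-9; baseline, primary endpoints". Neighbouring entries read differently, for example "Rumination (Ruminative Response Scale; RRS-short form; baseline, primary, secondary endpoints" and "Emotional wellbeing (The Short Warwick-Edinburgh Mental Well-being Scale; SWEMWBS; baseline, primary, secondary endpoints".

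The CHU-9 is the only quality-of-life instrument that Appendix I lists.

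**The concern.** A hypothesis about change from baseline to 4 months needs a 4-month measurement. H2 makes that prediction for quality of life, and the one instrument-by-visit list in the text reviewed does not provide the measurement.

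This cannot be put right at the analysis stage. Section 10 keeps the 4-month survey open for 7 days and ends participation once it is completed. A scale left out of that survey is lost for every participant, up to the planned 489. A statistical analysis plan can choose a model or a missing-data method, but it cannot supply a visit at which nobody was measured.

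**Working it through.** No sample size, power or alpha enters this point, so there is no planned figure to reproduce. The check sets H2 against the Appendix I list.

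**Step 1. Time points by outcome.** H2 requires baseline, 6 weeks and 4 months for each outcome.

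| H2 outcome | Instrument | Baseline | 6 weeks | 4 months |
|---|---|---|---|---|
| Anxiety | GAD-7 | yes | yes | yes |
| Psychological distress | DQ-5 | yes | yes | yes |
| Emotional wellbeing | SWEMWBS | yes | yes | yes |
| Rumination | RRS short form | yes | yes | yes |
| Emotion regulation | ERQ-CA | yes | yes | yes |
| CBT skill acquisition | CBTSQ | yes | yes | yes |
| Quality of life | CHU-9 | yes | yes | **not listed** |

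**Step 2. Count.** H2 has 7 outcomes × 2 follow-up times = 14 components. Appendix I supports 6 × 2 = 12 from the first six scales, plus 1 for the CHU-9 at 6 weeks, which makes 13. The shortfall is 14 − 13 = 1, or 1/14 = 7.1% of the components.

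**Step 3. Can the model fill the gap?** Section 10 analyses secondary outcomes with models similar to the primary one: a mixed-effects linear model, time-by-condition interaction, all available data, missing at random. The 4-month contrast for an app arm against control is

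(mean at 4 months − mean at baseline) in the app arm − (mean at 4 months − mean at baseline) in control.

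Under Appendix I the number of CHU-9 scores at 4 months is 0 in every arm. Neither 4-month mean is identified. A missing-at-random analysis borrows from participants who were observed at that visit, and here there would be none. The 6-week contrast uses only baseline and 6 weeks and can be estimated as planned.

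**Step 4. Do the other statements settle it?**

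- Section 10, read literally, repeats the whole 6-week battery at 4 months and so includes the CHU-9. But Appendix I restricts the digital alliance, satisfaction, barriers and recent-care questionnaires to the primary endpoint, so there the two batteries are meant to differ. The Section 10 paragraph also keeps calling the 4-month visit the primary endpoint assessment, which suggests wording carried over from the 6-week paragraph.
- The Section 4 sentence on using the same scales follows a list naming depression, anxiety, distress and wellbeing. Quality of life is not in that list, so the sentence does not clearly promise a 4-month CHU-9.
- The cross-references do not help. Section 10 places the baseline measures in Appendix D, the primary endpoint measures in Appendix E, and then, in the 4-month paragraph, the primary endpoint measures in Appendix D. Section 10.1 describes Appendix E as product information. Neither appendix is in the text reviewed.

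The contradiction is therefore between H2 and Section 10 on one side and Appendix I on the other, and nothing in the text reviewed resolves it.

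**The case against.** A reader might infer that the 4-month quality-of-life hypothesis simply cannot be tested, with the data missing by design. The documents do not support that, for three reasons.

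- Section 10, taken at its word, repeats the primary endpoint assessment at 4 months, which would include the CHU-9.
- Appendix I is the charter of the Trial Management Group, not a designated schedule of assessments, and it introduces its list as a partial one. Section 10 sends the reader to other appendices for the measures, and Appendix D may list the CHU-9 at 4 months.
- The charter departs from the body elsewhere. Section 11.1 puts items on hospitalisation and on self-identified deterioration in both follow-up assessments, and the charter list has no line for either. The charter asks about equivalent engagement where H3 predicts higher engagement with guidance. It treats digital therapeutic alliance as a moderator where H5 makes it a mediator.

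All of this stands as a limit on the claim. A time point missing from the charter list is weak evidence that the CHU-9 will not be given.

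It does not remove the contradiction. Appendix I is part of the protocol, names quality of life among its own research questions, and gives time points scale by scale. One scale has two time points where the six others have three. Whatever Appendix D says, at least one of H2, Section 10 and Appendix I has to change.

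**Conclusion.** The point holds as an internal contradiction with a conditional consequence. H2 and a literal reading of Section 10 imply a 4-month CHU-9, and Appendix I omits it. If the 4-month survey was built from Appendix I, one of seven H2 outcomes at one of two time points has no data and its contrast cannot be estimated. If the survey was built from Section 10, the data exist and only Appendix I is wrong.

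The reach is narrow. The primary outcome, the 6-week quality-of-life comparison and the other six secondary outcomes at both times are untouched. It still deserves correction because the loss, if it occurs, is permanent and the remedy is small. The conclusion assumes that the CHU-9 is the only quality-of-life measure, as Appendix I shows, and that no appendix outside the text reviewed has already settled the question.

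**What to change.** First check whether the CHU-9 is in the 4-month survey as built and in Appendix D. Then take one of two routes.

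1. **Keep H2 as written.** Include the CHU-9 in the 4-month survey and change its Appendix I entry to baseline, primary and secondary endpoints, like the other six scales. The cost is one added scale in an online survey that Section 10 puts at about 20 minutes, and a one-line edit.
2. **If the omission is deliberate.** Limit quality of life in H2 to the baseline-to-6-week comparison, and correct Section 10 so that it no longer describes the 4-month visit as the primary endpoint assessment. The cost is two short text edits and the loss of the 4-month quality-of-life comparison.

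Under either route leave research question 2 in Section 4 unchanged: it names quality of life without a time point and the 6-week data can answer it. If 4-month surveys have already closed without the CHU-9, only the second route remains for those participants.

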Primary analyses will be conducted to determine the effect of the interventions on depressive symptoms at the primary and secondary endpoints. Analyses will be undertaken on an intention-to-treat basis, including all participants randomised, regardless of intervention received. The effectiveness of the trial interventions will be established by a change on the PHQ-9-A between baseline and 6-weeks post-baseline (primary endpoint) and 4-month follow-up (secondary endpoint), based on the interaction between time and condition, using mixed-effects linear modelling with an unadjusted p value of 0.05. Effect sizes will be calculated based on differences in change scores between baseline and 6-weeks post-baseline, using standard deviations of the change scores pooled across conditions. This modelling will account for all available data, under the missing at random assumption. However, attrition analyses will be conducted to determine whether missing data is associated with any baseline demographics (age, gender), mental health status (symptom severity) or other descriptive variables. Any baseline variables identified as substantially imbalanced between groups will be added to the models on an exploratory basis to confirm the robustness of the findings to this imbalance. Where distributional assumptions cannot be satisfied, other modelling may be used to confirm the robustness of the findings. Similar models will be used for secondary outcomes. To analyse the effects of adherence on outcomes, the mixed-effects repeated measures linear modelling will be repeated using the categorical adherence measure as a between group factor (adheres v non-adheres v control). These results will be published in the primary outcomes paper. Exploratory analyses will examine evidence for moderation, that is, whether the intervention was more effective for certain subgroups of the sample. Further, exploratory analyses will also examine evidence for mediation, that is whether the effects of the intervention were driven by other variables.

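### Digital therapeutic alliance is a mediator in Section 4 but a moderator in Appendix I, and the listed 6-week measurement cannot support the moderator role

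*Protocol*

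**What the plan says.** Section 4 treats alliance as a mediator. H5 states that improvements in depressive symptoms among app users "will be mediated by rumination, emotion regulation, CBT skill acquisition, digital therapeutic alliance, and rates of engagement/completion", and research question 5 gives the same five factors. The H4 moderators are gender, age, "history of mental health, symptom severity at baseline, greater perceived need for care and higher levels of openness to digital mental health"; alliance is not among them.

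Appendix I restates the research questions differently. Question 9 asks whether factors including "openness to digital mental health, digital therapeutic alliance, perceived need for care, moderate the improvements in depressive symptoms". Question 10, on mediation, begins "Do factors such as CBT skill acquisition, emotion regulation, rumination, and program engagement/completion mediate the improvements" and does not name alliance.

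The Data list in Appendix I gives "Digital therapeutic alliance (Digital Working Alliance Inventory; D-WAI; primary endpoint", with no baseline or 4-month value. Other scales in that list have three time points, for example "Rumination (Ruminative Response Scale; RRS-short form; baseline, primary, secondary endpoints".

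Section 10 describes moderation as the intervention working better in some subgroups, and mediation as "whether the effects of the intervention were driven by other variables". It calls both analyses exploratory and does not say which mediator time is paired with which outcome time.

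**The concern.** A moderator in a randomised trial has to be fixed before treatment starts, so that arms can be compared within levels of it. The D-WAI score at 6 weeks can be affected by the allocated arm, by how much the programme was used and by how the participant felt by then. Comparing arms within high and low alliance would compare groups formed after randomisation, and an apparent subgroup effect could mislead.

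There is also a reason to settle the role in advance. Section 7 has the statistician unblinded for the moderator and mediator analyses, once the primary and secondary analyses are finished. If the protocol supports either role, the choice could be made with the main results known.

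A lesser matter concerns interpretation. Several H5 mediators have no value between baseline and the 6-week PHQ-A, so for that outcome a gain in skills or alliance cannot be told apart from a consequence of feeling better.

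**Working it through.** No stated figure is at issue, so the check sets the lists against each other and against the schedule.

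**1. Roles.**

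| | Section 4 | Appendix I |
|---|---|---|
| Alliance among moderators | No (H4; research question 4) | Yes (question 9) |
| Alliance among mediators | Yes (H5; research question 5) | No (question 10) |

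The two texts disagree in both rows. Both are current protocol text; neither is a log of changes.

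**2. Timing (Appendix I, Data).**

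| Measure | Baseline | During use | 6 weeks | 4 months |
|---|---|---|---|---|
| PHQ-A (outcome) | yes | no | yes | yes |
| D-WAI (alliance) | no | no | yes | no |
| CBT skills, emotion regulation, rumination | yes | no | yes | yes |
| Engagement/completion | – | logged automatically | – | – |

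**3. Moderator role.** Section 7 places randomisation immediately after the baseline assessment. The only listed D-WAI value comes 6 weeks later, so no pre-randomisation value exists and question 9 cannot be answered from it.

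**4. Mediator role.** Against the 6-week PHQ-A, the D-WAI and the three other questionnaire mediators are concurrent, so order is not established. Against the 4-month PHQ-A, all four precede the outcome. Engagement accrues before the 6-week assessment.

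**5. Illustration of the timing caution (all parameters assumed).** Take n = 326 (two arms of 163) and an arm effect of 0.35 on 6-week symptoms. The mediator is purely a consequence of 6-week symptoms with coefficient 0.5, residual SDs are 0.85, and there is no true mediation.

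- The mediator still differs by arm by 0.5 × 0.35 = 0.175.
- Its residual variance given arm and baseline is 0.5² × 0.85² + 0.85² = 0.903, so the SD is 0.950. The standard error of the arm difference is 0.950 × √(4/326) = 0.105, and z = 0.175/0.105 ≈ 1.66.
- The chance of significance is about P(Z > 1.96 − 1.66) = P(Z > 0.30) ≈ 0.38.

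A simulation of 600 runs declared mediation when both paths had p < 0.05:

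| Outcome model | False mediation |
|---|---|
| 6-week PHQ-A, adjusted for baseline | 39.7% |
| 4-month PHQ-A, adjusted for baseline only | 32.7% |
| 4-month PHQ-A, adjusted for baseline and 6-week PHQ-A | 1.5% |

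The top row agrees with the hand calculation. The bottom row is close to 0.05 × 0.40 = 2%, as expected when the second path is null. These figures show how the problem arises under one chosen scenario; they do not predict this trial's error rate.

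**The case against.** The strongest reply has four parts.

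- **The conflict sits in the Trial Management Group appendix and concerns exploratory hypotheses.** This stands, and it keeps the severity low. It does not remove the contradiction.
- **The timing rests on a summary list.** The appendices that Section 10 cites for the outcome measures are not available here, and the Appendix I list is incomplete: it names no scale for openness to digital mental health, which is an H4 moderator. This is a fair qualification of the statement that the D-WAI is taken only at 6 weeks. It is unlikely to rescue the moderator role, since participants receive their programme only after randomisation and could not rate an alliance with it beforehand.
- **The pairing of mediator and outcome times is commonly left to the SAP.** This stands. The protocol nowhere says that a 6-week mediator will be tested against the 6-week PHQ-A, so the timing point is a caution about interpretation and not an error in the text.
- **The lagged model changes the question.** This also stands. The 4-month PHQ-A adjusted for its 6-week value addresses later change, not what explains the 6-week effect.

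A reader might infer that every mediator is collected together with the 6-week outcome, or that alliance can be examined in neither role. The documents do not support this. Engagement is logged during use; the other three questionnaire mediators also have baseline and 4-month values; and the 6-week D-WAI precedes the 4-month PHQ-A.

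**Conclusion.** The contradiction over the role of alliance is real, and question 9 of Appendix I is wrong as written: on the listed schedule the D-WAI is a post-randomisation measure taken with the PHQ-A and cannot serve as a moderator. This rests on the Appendix I data list being right about D-WAI timing.

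The mediator role in H5 remains open to examination, with the caution that 6-week questionnaire mediators do not establish order against the 6-week PHQ-A. The simulated rates behind that caution depend wholly on assumed values.

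Severity is low. The analyses are exploratory, and the treatment comparisons on primary and secondary outcomes are untouched.

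**What to change.** In Appendix I, delete digital therapeutic alliance from the moderators in question 9 and add it to the mediators in question 10, so that both questions agree with H4 and H5. Deleting it from question 9 alone would leave question 10 at odds with H5. If outcomes are still shown by level of alliance, label the result a post-randomisation association.

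Add one sentence on interpretation: a result relating a 6-week questionnaire mediator to the 6-week PHQ-A does not establish temporal order. A supportive analysis is available from the listed measurements: the 6-week mediator, adjusted for its baseline where one exists, against the 4-month PHQ-A adjusted for baseline and 6-week PHQ-A.

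The cost is wording only, with no new measurement. The supportive analysis is less precise, because it loses participants who miss the 4-month assessment.
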